#### 6.1.2 Secondary Efficacy Analyses

All secondary efficacy analyses will be conducted among the mITT population using the same methodology as the primary efficacy analysis. A completer analysis is not planned for secondary efficacy analyses.

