9. STATISTICAL CONSIDERATIONS

9.1 Sample Size Determination

The primary efficacy endpoint is the proportion of participants with a \geq 1-stage improvement in fibrosis (as defined by NASH CRN Fibrosis Score) without worsening of NASH (as defined by the NAFLD Activity Score) at Week 48, as determined by liver biopsy.

It is planned to randomize approximately 100 participants to 1 of the 4 treatment groups (approximately 25 participants per group), BMS-986036 10 mg QW, BMS-986036 20 mg QW, BMS-986036 40 mg QW or matching placebo QW in a 1:1:1:1 ratio.

A Cochran-Armitage trend test of proportions, with an estimated response rate of 15% for the primary endpoint for placebo and response rates for BMS-986036 10 mg QW, BMS-986036 20 mg QW, and BMS-986036 40 mg QW of 20%, 30%, and 40%, respectively, would provide at least 70% power at a 1-sided $\alpha = 0.05$ (based on original sample size estimate of approximately 100 participants). The final sample size was approximately 155 participants (see Section 6.2).

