### 4.2 Secondary Efficacy Endpoints

The secondary efficacy endpoints are the proportion of participants with the following:

- Ishak Score  $>=1$  stage improvement at Week 48
- NASH CRN Fibrosis Score  $\geq 1$ -stage improvement (as defined by NASH CRN Fibrosis Score) in fibrosis without worsening of NASH or NASH improvement (reduction of NAS by  $\geq 2$  points with contribution from  $> 1$  NAS component) at Week 48
- $>= 1$ -stage improvement (as defined by NASH CRN Fibrosis Score) in fibrosis
- Any CPA decrease at Week 48
- NASH resolution (NAS component of ballooning = 0 and inflammation = 0-1) at Week 48
- NASH improvement (reduction of NAS by  $\geq 2$  points with contribution from  $> 1$  NAS component) at Week 48

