#### 6.1.1 Primary Efficacy Analysis

The primary efficacy endpoint is the proportion of participants who achieve a  $\geq 1$ -stage improvement (as defined by NASH CRN Fibrosis Score) in fibrosis without worsening of NASH (as defined by NAFLD Activity Score) at Week 48, as determined by liver biopsy.

Improvement in fibrosis is defined as a decrease of fibrosis by  $\geq 1$  point, as determined by the NASH CRN Fibrosis Score. Worsening of NASH is defined as an increase of the NAFLD Activity Score (NAS) by  $\geq 1$  point.

Participants will be stratified at randomization by country (Non-Japan versus Japan). Participants in countries other than Japan will be stratified at randomization according to Type 2 Diabetes Mellitus (T2DM) status (yes versus no). Japanese participants will not be further stratified.

If lack of response in the strata prohibits analysis, the strata may be reduced to Japan/Non-Japan only or no stratification at all.

Sponsor: Bristol-Myers Squibb

Protocol No.: MB130-069

A Cochran-Armitage trend test of proportions at a one-sided 0.05 level of significance will be used to examine the linear trend among the proportions across treatment groups. The null hypothesis states that there is no association between treatment level and fibrosis stage improvement. The alternative hypothesis states that there is an association between treatment level and fibrosis stage improvement.

The proportion of participants with response will be summarized by strata as well as overall for each treatment group. Shift tables will be presented for the NAFLD Activity Score and NASH CRN Fibrosis Score. A bar chart of response/non-response in the primary endpoint will be provided.

All participants who prematurely discontinue from treatment without a biopsy at Week 48 (or ET, if applicable) or otherwise have a missing Week 48 (or ET, if applicable) biopsy result will be considered non-responders for the primary analysis of the primary efficacy endpoint.

All biopsy results will be included in the participant listings.

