#### 6.1.1.1 Sensitivity Analyses

There will be a sensitivity analysis of primary efficacy endpoint to determine the effect of the stratification variables Japan and T2DM. A Logistic regression model will be used with randomized stratification factors as main fixed effects and NASH score at baseline as well as treatment. We will have all pairwise dose comparisons against placebo and trend test with a one-sided test at alpha = 0.05 with point estimate and two-sided 90% CI will be provided. Odds ratio point estimate and two-sided 90% CI. Average across the dose groups and comparison to placebo using a nominal one-sided test at alpha=0.05 will be calculated.

A sensitivity analysis using an extended Cochran Mantel-Haenszel (CMH) correlation test will be used to assess the trend among the proportions for treatment groups with an adjustment to strata. A two-sided 0.10 level of significance will be used.

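### The lead trend test for NASH resolution and NASH improvement leaves out baseline activity; stratifying on it would add about 1 to 8 points of power at 38 per arm, depending on a correlation the plan does not give

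*SAP*

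**What the plan says.** SAP 6.1.2 sets the rule for all secondaries: "All secondary efficacy analyses will be conducted among the mITT population using the same methodology as the primary efficacy analysis". The primary method in SAP 6.1.1 is: "A Cochran-Armitage trend test of proportions at a one-sided 0.05 level of significance will be used". That section names no covariate for the test.

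Two of the secondaries in SAP 4.2 are defined on NAS components. One is "NASH resolution (NAS component of ballooning = 0 and inflammation = 0-1) at Week 48". The other is NASH improvement: a fall in NAS of at least 2 points, with more than one component contributing.

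Baseline activity enters only in SAP 6.1.1.1, among the sensitivity analyses of the primary endpoint: "A Logistic regression model will be used with randomized stratification factors as main fixed effects and NASH score at baseline as well as treatment". The SAP does not define that score. The extended CMH test in the same section adjusts for the randomisation strata (Japan, T2DM), not for baseline activity. No planned model uses baseline ballooning or inflammation grade as a covariate. SAP 6.1.2 expressly drops only the completer analysis, so it is unclear whether the logistic model carries over to the secondaries.

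**The concern.** For these two endpoints, baseline limits the response by definition.

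- **Resolution** is a fixed state at Week 48. A participant at ballooning 1, inflammation 1 is one step away; one at ballooning 2, inflammation 3 is four steps away. Inclusion criterion 2 (Protocol 8.3.1) requires histology consistent with NASH and cirrhosis but no minimum grade. As written, it does not rule out someone who already meets the target at entry.
- **Improvement** asks the same 2-point fall of everyone, but baseline sets the room for it. A participant with only one non-zero component cannot respond at all.

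An unadjusted test treats this predictable variation as noise. Chance differences between arms in baseline activity also shift the observed dose trend. The SAP accepts the principle elsewhere: section 6.4 adjusts the continuous exploratory biopsy measures, such as CPA and qFibrosis, for their baseline value.

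Protocol 6.2.1 rests Phase 3 design and dose selection on the totality of efficacy, safety and PK from this study and its companion, so precision on these dose trends has some value.

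**Working it through.** **Inputs.** Protocol 9.1 gives "with an estimated response rate of 15% for the primary endpoint for placebo" and 20%, 30% and 40% for the three doses, tested one-sided at 0.05 with about 25 per arm. Protocol 6.2 gives the actual size: about 155 randomised, about 38 per arm. Rates for the NASH secondaries and their correlation r with baseline are not in the documents. The rates are borrowed from the primary, and r is varied.

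**Formula.** With scores s = 0, 1, 2, 3 (mean 1.5), n per arm and rates p:

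- T = n Σ(s − 1.5)p
- V0 = n p̄(1 − p̄) Σ(s − 1.5)²
- V1 = n Σ(s − 1.5)² p(1 − p)
- Power = Φ[(T − 1.645√V0)/√V1]

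**The plan's own figure.** At n = 25, T = 10.625, V0 = 24.20 and V1 = 22.98. Power = Φ[(10.625 − 8.092)/4.794] = Φ(0.528) = 70.1%. This reproduces the statement in Protocol 9.1 that the design "would provide at least 70% power at a 1-sided" α of 0.05.

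**Actual size, unadjusted.** At n = 38, T = 16.15, V0 = 36.78 and V1 = 34.94. Power = Φ[(16.15 − 9.976)/5.911] = Φ(1.044) = 85.2%.

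**Adjusted, closed form.** A baseline measure with correlation r multiplies the effective n by 1/(1 − r²), so T is multiplied by 1/√(1 − r²) relative to its standard error. At r = 0.5: Φ[(16.15 × 1.1547 − 9.976)/5.911] = Φ(1.467) = 92.9%.

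**Check by simulation.** 40,000 trials per setting at 38 per arm, three equally likely baseline levels, logistic relation, marginal rates held fixed, Cochran-Armitage test against the CMH correlation test stratified by level:

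| r | Closed form, from 85.2% | Simulated, unadjusted → stratified | Odds ratio per level needed |
|---|---|---|---|
| 0 | no change | 85.9 → 85.3 | 1.0 |
| 0.2 | 86.5 (+1.3) | 85.8 → 86.6 | 1.8 |
| 0.3 | 88.0 (+2.8) | 85.6 → 87.9 | 2.5 |
| 0.4 | 90.2 (+5.0) | 85.7 → 90.3 | 3.8 |
| 0.5 | 92.9 (+7.7) | 85.8 → 93.4 | 6.6 |

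At r = 0.5 the implied response by level, at the mean rate of 26%, is about 3%, 17% and 58%.

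**Rare responses.** With 5/8/12/18% the closed form gives 60.5% unadjusted and would suggest 71.3% at r = 0.5. That correlation is not attainable here. If every response fell in the top third, the covariance would be 0.1075 (the mean rate). The SD of a −1/0/1 score is 0.816, and the within-arm SD of response is √0.0936 = 0.306, so r is at most 0.1075/(0.816 × 0.306) = 0.43. Simulated power moves from 62.5% to 62.6% at r = 0.2 and from 62.6% to 65.1% at r = 0.3. At r = 0.4 it moves from 62.4% to 69.5%, but that needs nearly all responders in one level (odds ratio about 23 per level). At r = 0 it falls from 62.6% to 61.2%.

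**Type I error.** In the same runs under no dose effect, the stratified test rejected in 4.9% to 5.1% of trials at 38 per arm.

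**Chance imbalance.** Take illustrative response rates of 50%, 25% and 5% in three equal baseline groups (r about 0.42). The between-group variance is [(0.233)² + (0.017)² + (0.217)²]/3 = 0.034. Imbalance alone then gives a placebo versus 40 mg difference an SD of √(2 × 0.034/38) = 0.042, about 4 percentage points.

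**The case against.** **Validity.** An unadjusted trend test in a randomised trial is valid, and its error rate already covers chance imbalance. These are secondaries with no power target, in a Phase 2 trial without multiplicity control. All of that stands. A reader might infer bias or a false-positive problem; the documents support neither.

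**Size.** A reader might take the loss to be 8 to 11 points. The 11 (70.1% to 80.8%, r = 0.5) belongs to the superseded 25 per arm, and r = 0.5 has no source in the documents. It needs a strong relation, as the table shows. Counting missing biopsies as non-response weakens it further: if 15% were missing unrelated to baseline (an assumption), an overall r of 0.5 would need about 0.56 among those biopsied.

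**Mechanism.** It is tempting to say that baseline sets how far everyone must move. That fits resolution only, because the fall required for improvement is the same for all. The directions also differ: high baseline activity makes resolution harder but leaves more room for improvement. One correlation need not serve both.

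**Already covered?** The logistic model in SAP 6.1.1.1 includes a baseline NASH score and could be read as extending to the secondaries, and the planned NAS shift tables will show imbalance. But that model is worded for the primary endpoint, its score is undefined, and on either reading it is a sensitivity analysis rather than the lead test.

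**Conclusion.** The point holds as an efficiency gain. The lead test of both NASH secondaries ignores a measured baseline characteristic that bounds the response by construction. At 38 per arm, using the primary's rates, adjustment is worth about 1, 3, 5 and 8 points of power at correlations 0.2, 0.3, 0.4 and 0.5. With rare responses the gain is about 0 to 3 points, short of near-complete separation by baseline level. Both the rates and the correlation are assumptions, so no single figure can be attached to this trial. The SAP does not disregard baseline activity altogether; it confines it to a sensitivity model and leaves unsaid whether that model reaches these endpoints.

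**What to change.** In SAP 6.1.2, before unblinding:

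1. Make the lead dose-trend test for NASH resolution and NASH improvement the extended CMH correlation test, stratified by a few prespecified baseline-activity levels: NAS total for improvement, ballooning and inflammation grade for resolution.
2. State that the logistic model of SAP 6.1.1.1 is supportive for these endpoints, uses the same covariate, and replaces the undefined baseline score with that definition.
3. Keep the crude proportions and the Cochran-Armitage test as supportive, and leave missing = non-responder unchanged.
4. Give a rule for collapsing sparse levels, set without reference to treatment.

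No new data are needed. The CMH method is already in the SAP, but the baseline-activity strata are new and must be written for each endpoint. If baseline proves unrelated to response, power may fall by up to about 1 point.

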#### 6.1.3 Adjustment for Multiplicity

Since this is a Phase 2 study, no adjustment for multiplicity will be applied.

### 6.2 Safety Analyses

Safety analyses will be conducted using the safety population.

#### 6.2.1 Adverse Events

All adverse events will be presented by treatment group and pooled BMS-986036.

A summary of treatment-emergent AEs, including the number of events reported and the number and percentage of participants reporting

- at least one AE
- any severe AE
- any treatment-related AE
- any AEs of special interest
- any severe treatment-related AE
- any AE with outcome of death

Sponsor: Bristol-Myers Squibb

Protocol No.: MB130-069

- any serious AE
- any treatment-related SAE
- any AE leading to the discontinuation of study treatment
- any treatment-related AE leading to the discontinuation of study treatment
- any AE leading to discontinuation of the study
- any treatment-related AE leading to discontinuation of the study

A breakdown of the number and percentage of participants reporting each AE, categorized by system organ class (SOC) and preferred term (PT) will be presented. Maximum severity will be summarized for all TEAE by SOC and PT. Counts for AEs will be by participant not event and participants are only counted once within each SOC or PT. AEs of special interest will be tabulated by event category and preferred term.

Only treatment-emergent AEs will be summarized in tables. All AEs will be included in listings.

### **6.2.2 Deaths and Serious Adverse Events**

A summary of treatment-emergent SAEs, categorized by SOC and PT will be presented. Counts will be by participant, not event, and participants are only counted once within each SOC or PT. All treatment-emergent SAEs and all SAEs will be listed.

Treatment-emergent AEs with an outcome of death will be summarized by SOC and PT. All treatment-emergent AEs with an outcome of death will be listed.

### **6.2.3 ECGs, Vital Signs, and Physical Examinations**

Based on the safety population, vital sign and 12-lead ECG parameters will be summarized by visit, treatment group, and pooled BMS-986036. All vital signs and ECG results will be listed.

ECG results will be summarized for continuous variables and will be presented for the absolute result and change from baseline. QTcF values will be presented with the implementation of corrections (i.e., Fridericia's) as defined in ICH Guidelines E14 by the following categories:

- Absolute QTcF interval prolongation:
  - QTcF interval > 450ms
  - QTcF interval > 480ms
  - QTcF interval > 500ms
- Change from baseline in QTcF interval:
  - QTcF interval increases from baseline >30ms
  - QTcF interval increases from baseline >60ms.

Physical examination results and other safety data will be listed.

### **6.2.4 Clinical Laboratory Parameters**

Based on the safety population, continuous laboratory results will be summarized by visit, treatment group, and pooled BMS-986036 (in both SI units and US Conventional units). Categorical results such as those for urinalysis will be summarized by number and percentage of participants in each category. These summaries will be based on central laboratory results, except in rare circumstances in which only a local lab value is available then a local lab value may be used. This value will be presented in the same unit and summarized with the central results from other participants. Summaries will present both actual and change-from-baseline results for continuous values.

Sponsor: Bristol-Myers Squibb

Protocol No.: MB130-069

Altered postbaseline values will be descriptively summarized by counts and percentages of participants ever experiencing specified altered values at any postbaseline time point.

Laboratory values below the lower limit or above the upper limit of quantification will be imputed to the lower or upper limit, respectively, for summary tables. The actual values will be displayed in the listings.

Box plots will be presented by time point. All laboratory data specified in the summary tables will be present in listings.

### **6.2.5 Bone Mineral Density Testing (BMD)**

BMD data will be summarized by visit, treatment group, and pooled BMS-986036. In rare circumstances where the number of evaluable lumbar spine segments changes over time for bone mineral density results, only participants with the same number and same segments as their baseline assessment will be included in change from baseline summaries of lumbar spine values. In addition, only participants with at least 2 evaluable lumbar spine segments at baseline will be included in the summary of the baseline time point. All bone mineral density results will be listed. Once available, the quality control (QC)-corrected values of BMD and t- and z-scores produced will be analyzed.

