6.1.1 Nonclinical Studies

The effects of BMS-986036 treatment have been evaluated in both prevention and therapeutic intervention studies in a mouse model of NASH, in which mice develop a fatty liver at 5 weeks of age, NASH at 7 weeks of age, and liver fibrosis at 9 weeks of age.^{14,15}

- In the prevention study, 5-week-old mice treated with BMS-986036 had significantly reduced body weight, liver weight, liver-to-body weight ratio, plasma TGs, and liver TGs. BMS-986036 also significantly decreased histological evidence of hepatic perturbations (NAFLD Activity Score, comprising assessments of steatosis, lobular inflammation, and hepatocyte ballooning) and significantly reduced fibrosis, demonstrating an anti-fibrotic effect of BMS-986036. Consistent with this observed anti-fibrotic effect, BMS-986036 treatment reduced hepatic expression of alpha-smooth muscle actin, tissue inhibitor of metalloproteinases 1 (TIMP-1), and type 1 collagen.
- In the therapeutic intervention study, 9-week-old mice treated with BMS-986036 had statistically significant decreases in liver-to-body weight ratio, blood glucose, plasma alanine aminotransferase (ALT), liver lipid content (TG and cholesterol), as well as histological evidence of hepatic steatosis, hepatocyte ballooning, lobular inflammation, and fibrosis.

BMS-986036 was not genotoxic and had no adverse effects on cardiovascular, respiratory, and/or central nervous systems in rats, dogs, and/or cynomolgus monkeys. BMS-986036 was neither embryo-lethal nor teratogenic in definitive rat or rabbit embryo-fetal development studies.

In repeat-dose toxicity studies in rats and sexually mature monkeys up to 6 months in duration, BMS-986036, administered once daily (QD), was clinically well tolerated and evidence of pharmacology was observed at all doses (changes in adiponectin and other metabolic parameters). Effects on bone (decreases in bone mass, size, mineralization, and strength, as well as changes in formation/resorption biomarkers) were observed, and these

were attributed to pharmacologically mediated body weight loss/reductions and slower overall growth, except at the highest dose tested in monkeys (1 mg/kg/day; 19 \times area under the concentration-time curve [AUC] multiple).

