7.3 Safety Objective

To demonstrate the safety of BMS-986036 in adults with NASH and compensated cirrhosis throughout the course of the study, including BMD and immunogenicity.

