9.5.3 Safety Analyses

Safety analyses will be performed using the As Treated population. For analysis, all treatment-emergent (i.e., occurring after the first dose of study medication) AEs, SAEs, and AEs of special interest will be summarized by system organ class, preferred term, and treatment. Vital signs, immunogenicity, BMD, and laboratory data will be summarized by treatment. ECG abnormalities, physical examination abnormalities, if present, will be summarized.

Responses of anti-BMS-986036 antibodies and anti-FGF21 antibodies will be listed and tabulated by treatment and study day. [REDACTED]

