#### 3.3 Safety Objectives

The safety objectives of this study are to demonstrate the safety of BMS-986036 in adults with NASH and compensated cirrhosis throughout the course of the study, including bone mineral density and immunogenicity.

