#### 4.3.6 Bone Mineral Density Testing (BMD)

BMD as measured by DXA scans of the hip (including femoral neck) and spine that will be performed during the Screening Period and at the Week 48 Visit (or ET, if applicable) as indicated in the Schedule of Activities (protocol [Section 1](#)). Participants will return for a follow-up DXA assessment 6 months (1 month is defined as 4 calendar weeks) after the Week 52/PTFU Visit. DXA may be performed within a window of ± 7 days of the scheduled Week 48/ET Visit and within a window of ± 14 days of the scheduled 6-month follow-up visit. DXA scans will be evaluated by central reading. Following will be summarized.

- Absolute and change from baseline values

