For continuous endpoints the analysis of covariance (ANCOVA) models will be used to explore changes from baseline that include fixed factors for the treatment group and the corresponding covariate for baseline value for the following:

- Quantitative measurements of fibrosis and fat on biopsy
  - Assessment of qFibrosis using digital pathology
  - Assessment of CPA
  - Assessment of fat and alpha-SMA by morphometry
- Hepatic fat fraction as measured using MRI-PDFF
- Noninvasive measures of fibrosis and/or cirrhosis
  - Liver stiffness as determined by MRE
  - Fibroscan elastography results
  - APRI, FIB-4, and NAFLD scores
- Exploratory biomarkers
  - Transaminases ALT and AST
  - PRO-C3

A repeated measures analysis will model changes from baseline for each of the exploratory endpoints separately for data collected at planned visits using restricted maximum likelihood estimations. The model will include treatment group, visit, baseline value, treatment \* visit and baseline stratification factors as fixed effects. An unstructured covariance matrix will be used to represent the correlation of the repeated measures within each subject. This model will be used to provide point estimates for the treatment differences, standard errors for the differences, and corresponding 2-sided 95% confidence intervals for mean change from baseline at each time point. Statistical inferences for comparing treatment groups will utilize Kenward-Rodgers Degrees of Freedom.

Other biomarkers will be descriptively summarized by time point and will include percent change from baseline in addition to change from baseline.

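### BMD is part of the safety objective, but the planned BMD analysis reports no difference from placebo, no confidence interval and no baseline adjustment

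*SAP*

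**What the plan says.** **Objective.** Protocol 7.3 reads: "To demonstrate the safety of BMS-986036 in adults with NASH and compensated cirrhosis throughout the course of the study, including BMD and immunogenicity". SAP 3.3 repeats it ("throughout the course of the study, including bone mineral density and immunogenicity").

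**Why bone is there.** Protocol 6.1.1 reports, from the repeat-dose animal studies, "Effects on bone (decreases in bone mass, size, mineralization, and strength", together with changes in bone biomarkers. Protocol 6.3.2.4 lists effects on bone among the risks, and Protocol 8.5.3.7 makes bone-related events adverse events of special interest. DXA of hip and spine is done at Screening, at Week 48 or early termination (ET), and 6 months after the Week 52/PTFU visit (Protocol 8.5.3.8).

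**Analysis.** Protocol 9.5.3: "Vital signs, immunogenicity, BMD, and laboratory data will be summarized by treatment". SAP 4.3.6 names the quantities: "Absolute and change from baseline values". SAP 6.2.5: "BMD data will be summarized by visit, treatment group, and pooled BMS-986036". The same section adds listings, a rule on matching lumbar segments, and the statement that the QC-corrected values of "BMD and t- and z-scores produced will be analyzed", without naming a model, contrast or interval.

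**What a summary contains.** SAP 6.5 defines it for continuous data as n, mean, SD, median, quartiles, minimum and maximum.

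**Where treatment differences are estimated.** SAP 6.4 opens its modelling paragraph with "For continuous endpoints the analysis of covariance (ANCOVA) models will be used to explore changes from baseline", followed by a closed list of endpoints. It then describes a repeated-measures model for exploratory endpoints that gives treatment differences with two-sided 95% intervals. BMD is in neither.

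**The concern.** An objective to demonstrate safety on a named risk asks for an estimate of the drug effect on that risk and its uncertainty. The trial has a concurrent placebo arm and dedicated scans before, at the end of, and after 48 weeks of dosing. The earlier human BMD data in Protocol 6.3.2.4 cover only 12 or 16 weeks of dosing. Yet the plan never sets BMD change on drug against BMD change on placebo. It does so, with intervals, for exploratory measures such as FibroScan and ALT.

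A report could then conclude that there was no meaningful BMD difference from side-by-side arm means, without showing whether the data exclude a loss of 1 point or only of 3. Protocol 6.2.1 says that Phase 3 design and dose selection will use the totality of efficacy, safety and PK data, so the precision of the bone result matters to a later decision.

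**Working it through.** **1. Is there a figure in the plan to reproduce?** Not for BMD: neither document gives an SD, a margin, or a precision or power statement. The only power figure is for histology (Protocol 9.1: at least 70%, Cochran-Armitage, 25 per arm, rates 15/20/30/40%, one-sided 0.05). It reproduces. With centred scores -1.5, -0.5, 0.5, 1.5:
- signal = 25 × (-0.225 - 0.100 + 0.150 + 0.600) = 10.625
- null SD = √(0.2625 × 0.7375 × 25 × 5) = 4.919
- alternative SD = √(25 × 0.9194) = 4.794
- power = Φ[(10.625 - 1.645 × 4.919)/4.794] = Φ(0.528) = 70.1%

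This says nothing about BMD.

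**2. What interval would the trial give?** Inputs: about 38 per arm (Protocol 6.2), so 3 × 38 = 114 on pooled drug. The SD of percent change in BMD is my assumption, 2% to 5% of baseline.

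Half-width = t × SD × √(1/n₁ + 1/n₂)
- one dose v placebo: √(1/38 + 1/38) = 0.2294, t(74 df) = 1.993
- pooled v placebo: √(1/114 + 1/38) = 0.1873, t(150 df) = 1.976

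For SD 3%, this is 1.993 × 3 × 0.2294 = 1.37 and 1.976 × 3 × 0.1873 = 1.11.

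The last two columns give the loss excluded with 80% power if the true difference is zero: (1.960 + 0.842) × SD × the same root.

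| Assumed SD | 95% half-width, one dose | 95% half-width, pooled | Excludable loss, one dose | Excludable loss, pooled |
|---|---|---|---|---|
| 2% | 0.91 | 0.74 | 1.29 | 1.05 |
| 3% | 1.37 | 1.11 | 1.93 | 1.57 |
| 4% | 1.83 | 1.48 | 2.57 | 2.10 |
| 5% | 2.29 | 1.85 | 3.21 | 2.62 |

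All entries are percentage points, before any gain from baseline adjustment.

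**3. Missing scans.** There is no ET or follow-up DXA for participants who stop before completing Week 16 (Protocol 8.5.3.8), and no dropout rate is stated. With 30 evaluable per arm (assumed), the half-widths become 1.03 to 2.58 per dose and 0.83 to 2.09 pooled.

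**4. Is 38 per arm enough?** Take a 2-point loss purely as an illustration. Excluding it with 80% power needs 16, 36, 63 or 99 per arm for SD 2, 3, 4 or 5%. The answer turns on an SD that the documents do not give, which is why the observed interval should be reported.

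**The case against.** The strongest reply is that descriptive safety tables are normal in Phase 2. Protocol 9.5.3 and SAP 6.2.3 to 6.2.6 agree with each other, immunogenicity sits in the same objective and is also only summarised, and nothing is biased. That stands as far as it goes: this is an omission of an estimate, not an error.

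Several stronger readings are tempting and should not be drawn.
- *The trial cannot say how much bone loss it rules out.* It can, roughly. Change from baseline is tabulated by arm with n, mean and SD, so an unadjusted difference and interval can be derived. They would not be adjusted for baseline BMD or strata. They would also be in absolute units, since percent change is not a listed BMD quantity.
- *There is a separate bone-safety objective.* There is one overall safety objective that includes BMD.
- *Bone loss is the main nonclinical finding.* The protocol does not rank the findings. Section 6.1.1 attributes the bone effects to weight loss and slower growth, except at the highest monkey dose. Section 6.3.2.4 suggests no effect on BMD after 12 or 16 weeks in two Phase 2 studies.
- *Arm means are the only bone evidence.* T- and z-scores, listings, bone-related adverse events and DMC oversight are also planned. None of them gives a BMD difference from placebo.
- *The trial is too small for BMD.* This cannot be judged without an SD and a margin.

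One could also argue that BMD, being continuous, falls under the SAP 6.4 ANCOVA. The list that follows does not contain it, and SAP 4.3 classes it as a safety endpoint. The table shells are a separate document that was not available; they may hold more, but the SAP text should specify the analysis.

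**Conclusion.** The point holds in a limited form. The objective is to demonstrate safety including BMD, and the written plan gives no difference from placebo, no interval and no baseline adjustment for BMD, so the planned analysis does not show how much bone loss is excluded. The information needed is collected; what is missing is a pre-specified estimate.

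The likely size of the unreported uncertainty is a 95% half-width of about 0.9 to 2.3 points per dose and 0.7 to 1.9 points pooled. This rests on the assumed SD of 2% to 5% and on all 38 per arm being evaluable. Missing scans widen it, and baseline adjustment may narrow it. No claim is made that a relevant loss would be missed, because the documents define none.

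**What to change.** In SAP 6.2.5, add for lumbar spine, total hip and femoral neck:
- An ANCOVA of change, and of percent change, in BMD with treatment, baseline BMD and the randomisation strata (Japan; non-Japan with T2DM; non-Japan without T2DM). The SAP 6.4 ANCOVA has treatment and baseline only, so the strata term must be written in.
- Each dose minus placebo and pooled BMS-986036 minus placebo, with two-sided 95% intervals and no hypothesis test. Keep the existing lumbar-segment rule.
- Week 48 reported in the Week 52 analysis (SAP 7.1), and the 6-month scan in the long-term follow-up analysis (SAP 7.2).
- ET scans, which can fall anywhere from Week 16 on, kept apart from Week 48, as SAP 6.4 does for non-biopsy endpoints. Add a sensitivity analysis that includes them.

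The cost is a little programming with model types already in the SAP. No visit, scan or participant is added. If the change comes after unblinding, label it as such in the study report, in line with SAP 7.3. If the sponsor prefers to keep BMD descriptive, the least change is to reword the objective so that it describes BMD rather than demonstrates safety on it.
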